8.3.6 Adverse Events of Special Interest

Adverse Events of Special Interest (AESI) for this study include:

- AEs of possible remote spread effect of toxin
- AEs suggestive of hypersensitivity reaction.

These events must be collected in the eCRF.

If they meet the seriousness criteria, they should also be reported as SAEs (refer to Appendix 10.3).

Adverse events of special interest are AEs that may not be serious but are of special importance to a particular drug or class of drugs. Such events might be precursors to more serious medical conditions, for example, muscle pain and elevated creatine phosphokinase may be indicative of potential rhabdomyolysis.

Other types of nonserious events may be important in and of themselves, such as those that could affect quality of life in a meaningful way (e.g. impotence, hair loss).

Adverse events of special interests with BoNT are events that suggest a possible remote spread effect of the toxin and are presented by function in Section 10.4 (Appendix 4). These symptoms could be related to toxin spread and in case of occurrence they should be reported and monitored carefully until resolution. AEs suggestive of hypersensitivity reaction are also of special interest and will be analysed using the Medical Dictionary for Regulatory Activities (MedDRA) Hypersensitivity standardised MedDRA queries (SMQ) (narrow). All AEs will be monitored by the sponsor to determine if they meet the criteria of AESIs.

8.3.7 Reporting of Study Intervention Errors Including Misuse/Abuse

- Medication errors are unintentional errors in the prescribing, dispensing, administration or monitoring of a study intervention (medicinal product) while under the control of a healthcare professional, participant or consumer (European Medicines Agency definition).
- Misuse refers to situations where the study intervention is intentionally and inappropriately used not in accordance with the protocol.
- Abuse corresponds to the persistent or sporadic, intentional excessive use of a medicinal product, which is accompanied by harmful physical or psychological effects.
- Study intervention errors and uses outside of what is foreseen in the protocol will be recorded in the eCRF irrespective of whether associated with an AE/SAE or not. It will also be documented in the AE section of the eCRF if associated with an AE. It will be reported in the safety database only if associated with an SAE.
- Misuse or abuse will be collected and reported in the safety database, whether associated or not with an AE/SAE, within 24 hours of investigator's awareness.

8.4 Pharmacokinetics

Pharmacokinetic parameters are not evaluated in this study.

8.5 Genetics

Genetics are not evaluated in this study.

8.6 Biomarkers

Biomarkers are not evaluated in this study.

8.7 Immunogenicity Assessments

Immunogenicity is not evaluated in this study.

8.8 Health Economics OR Medical Resource Utilization and Health Economics

Health Economics or Medical resource utilization and health economics parameters are not evaluated in this study.

9 STATISTICAL CONSIDERATIONS

9.1 Statistical Hypotheses

The primary endpoint, CMAP total amplitude at Week 28, measured as relative change from Baseline (%), will be analysed using a mixed-effects model for repeated measures (MMRM), $\delta_{db} = \mu_{dysport} - \mu_{botox}$ and $\delta_{dx} = \mu_{dysport} - \mu_{xeomin}$ are the contrasts (i.e. mixed model Wald tests) of the Dysport versus Botox versus Xeomin comparisons in the primary endpoint at Week 28 of the study. Two elemental null hypotheses will be investigated,

$$H_{0,db,1} : \delta_{db} = 0 \text{ and}$$

$$H_{0,dx,1} : \delta_{dx} = 0.$$

These null hypotheses of no difference between the respective treatment arms in the primary endpoint will be tested against the respective two-sided alternative hypotheses

$$H_{A,db,1} : \delta_{db} \neq 0 \text{ and}$$

$$H_{A,dx,1} : \delta_{dx} \neq 0$$

at a 5% significance level ($\alpha = 0.05$) using a MMRM model and mixed model Wald tests of the respective contrast the Dysport versus Botox versus Xeomin comparisons in the primary endpoint at Week 28 of the study.

To control for the family-wise type I error rate at the two-sided level $\alpha = 0.05$, a Hochberg procedure [Dmitrienko and D'Agostino 2013] will be applied to investigate the two null hypotheses $H_{0,db,1}$ and $H_{0,dx,1}$. The testing procedure uses the following decision rules for the two p-values p_{db} and p_{dx} :

- Both null hypotheses are rejected if $\max(p_{db}, p_{dx}) \leq \alpha$
- Only the null hypothesis corresponding to the smaller p-value $\min(p_{db}, p_{dx})$ is rejected if $\min(p_{db}, p_{dx}) \leq \alpha/2$ and $\max(p_{db}, p_{dx}) > \alpha$.

If both null hypotheses of the primary endpoint are rejected, then the same Hochberg procedure will be applied sequentially to the two respective null hypotheses comparing Dysport with Botox and with Xeomin for secondary endpoints in the following order:

1. CMAP total amplitude at Week 40 post-injection
2. Incidence of recovery of CMAP total amplitude at Week 28 post-injection
3. Incidence of recovery of CMAP total amplitude at Week 40 post-injection

The two null hypotheses of secondary endpoint k , $k = 2, 3$ are tested with a Hochberg procedure, when both null hypotheses of endpoint $k-1$ are rejected.

9.2 Sample Size Determination

Approximately 48 participants will be screened to achieve 15 participants randomised to Dysport, 15 participants randomised to Botox and 15 participants randomised to Xeomin using a 1:1:1 randomisation ratio and assuming a screening failure rate of 5%.

The sample size calculation is based on the primary efficacy estimand and its endpoint relative change from baseline in EDB CMAP total amplitude at Week 28. Using a 2-sided t-test at the 5% significance level, the chosen sample size provides at least 88% power to detect a treatment difference of 18% relative change from baseline in the Dysport arm than in a comparator arm assuming a common standard deviation in all treatment arms of 15% as observed for Dysport in a historical study CCI – Part B. The treatment difference is based on the observed average EDB CMAP total amplitude at 6 months of Dysport 40 U (CCI – Part B) and of Botox and Xeomin 16 U in Wohlfarth [Wohlfarth 2007]. The power analysis was conducted with NQuery version 8.4.1.0. Given the made assumptions and the sample size of 15 participants per arm the probability to show superiority of Dysport to both comparators

simultaneously is at least 81%, as shown in a simulation study conducted with software R version 4.0.3.

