6.3 Measures to Minimize Bias: Randomisation and Blinding

6.3.1 Randomisation

The sponsor’s randomisation manager who is a statistician independent of the study will prepare the list of randomisation numbers for this study. It will be produced in blocks, on a balanced ratio [1 Dysport: 1 Botox: 1 Xeomin].

After eligibility is confirmed at Day 1, participants will be assigned a randomisation number and to the associated study intervention group, in sequential order within the centre. Each participant will be treated with the intervention allocated to this randomisation number. This will be done by an unblinded pharmacist (independent reconstitutor) in charge of the study intervention preparation, by considering the first unused treatment allocation envelope among the set of envelopes provided to the centre. The assigned randomisation number will have to be specified on the treatment kit, vial and syringe used for the study intervention reconstitution.

The investigator, the unblinded pharmacist, and investigator staff will under no circumstances change the randomisation number or the study intervention group allocated to the participant.

Recruitment will stop once 45 participants have been randomised. Randomised participants who terminate their study participation for any reason before starting intervention will retain

their randomisation number (the randomisation number will not be reused). The next participant will be assigned the next randomisation number.

Randomised participants who discontinue the study early will not be replaced.

The sponsor's randomisation manager will keep the master list of randomisation numbers. Access to this list must be restricted until authorisation is given to release it for final analysis.

6.3.2 *Maintenance of Blinding*

During the study, the sponsor, investigator (including study site personnel) and the participant will be blinded to the study intervention. To maintain the blind during the study only a qualified, trained and unblinded person independent of the injector and investigator will prepare (i.e. reconstitute) the study intervention and will have no further involvement in the study. This person will be fully trained in the method of preparing the study intervention and the importance of their role in maintaining the blind for the participant, the investigator and the rest of the team.

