7 DISCONTINUATION OF STUDY INTERVENTION AND PARTICIPANT DISCONTINUATION/WITHDRAWAL

7.1 Discontinuation of Study Intervention

In this study, there will be only one treatment cycle administered on Day 1 of the study, thus discontinuation of the study intervention is not applicable. In the event, a participant is randomised, but does not receive study intervention, the participant will not remain in the study and the EoS/EW assessments will not be performed

7.1.1 *Temporary Discontinuation*

In case of suspected or confirmed COVID-19 (SARS-CoV-2) infection at the Baseline visit (Day 1), the study intervention administration may be temporarily postponed depending on the participant's clinical presentation. In some cases, the investigator may request a participant be retested before the intervention administration is administered.

In the event of suspected or confirmed COVID-19 infection after study intervention administration on Day 1, the participant will be required to isolate for at least 14 days and have a negative SARS-CoV-2 test before returning to the study site for the next follow-up visit. A participant may be permanently discontinued at the discretion of the investigator if further study participation is deemed to be harmful for the participant, or other participants in the study and/or study site personnel.

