9.3 Analysis Sets

For the purposes of analysis, the following analysis sets are defined:

Participant Analysis Set	Description
Screened	All participants who signed an informed consent form
Randomised	The randomised set will contain all participants who are randomised to study treatment. A participant will be considered as randomised if a study intervention group has been randomly assigned. For analyses and displays, participants will be classified according to randomised treatment
Safety	The safety set will contain all participants who receive at least one dose of study medication. For analyses on the safety set, participants will be classified according to treatment received. If there is any doubt whether a participant was treated or not, he will be assumed treated for the purposes of analysis.
Pharmacodynamic (PD)	The PD analysis set will contain all participants from the randomised set who receive the appropriate dose of study treatment and have CMAP recorded for baseline and at least one post baseline assessment.

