5.7.2 Analysis of Primary Pharmacodynamic Endpoint

5.7.2.1 Endpoint, Treatment Effect and Estimand Definition

To assess the primary objective, the primary estimand has the following key attributes:

- Population of interest: healthy adult male participants as defined by the listed inclusion/exclusion criteria in Section 5.1 and 5.2 of the protocol.
- Variable/endpoint of interest: CMAP total amplitude at Week 28, measured as percentage relative to baseline (%), calculated as [value at Week 28 (mean of the three measurements/baseline value (means of the six measurements)]*100.

- ICEs are the following:
 - a) Study discontinuation
 - b1) PDs with potential impact on relevant CMAP total amplitude assessments (i.e. participant received the wrong study intervention and CMAP at Week 28 performed out of a specified time window ($> +/- 2$ weeks))
 - b2) PDs with no expected impact on relevant CMAP assessments (e.g. other time window violations, PDs related to covid-19)
- Treatment regimen: Dysport, Botox or Xeomin will be administered as described in Section 6 of the protocol and potential intake of permitted concomitant medications (for a list see Section 6.8 of the protocol).
- Population-level summary of the treatment effect of interest: the difference in average percentage relative to baseline in each study intervention group in CMAP total amplitude at the respective timepoint.

For ICEs (a) and (b1) a hypothetical strategy will be used, the treatment difference which would have been measured if the ICE would not have happened is of interest and will be assessed taking into account the long term pharmacodynamic effect of the investigated compounds. This implies that assessments after the occurrence of a major protocol deviation interfering with CMAP total amplitude will be ignored for the primary analysis. No imputation of missing CMAP will be done (MMRM analysis, please refer to [section 5.7.1.2](#)). For ICEs (b2), a treatment policy will be used.

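### Are the stated power figures of 88% and 81% wrong because nothing is allowed for loss before Week 28?

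*Protocol*

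**What the plan says.** Protocol section 9.2, repeated in SAP section 2.3, states that "the chosen sample size provides at least 88% power to detect a treatment difference of 18% relative change from baseline", with a common SD of 15% and the test described as "Using a 2-sided t-test at the 5% significance level". The probability of showing superiority to both comparators "simultaneously is at least 81%, as shown in a simulation study conducted with software R version 4.0.3"; that sentence names 15 participants per arm as its basis. The only attrition term is a 5% screening failure rate, which takes about 48 screened to 45 randomised.

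Other sections fix how many of the 45 can contribute at Week 28:

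- Protocol 6.3.1: "Recruitment will stop once 45 participants have been randomised", and "Randomised participants who discontinue the study early will not be replaced".
- Protocol 7.1, on someone randomised but not dosed: "the participant will not remain in the study and the EoS/EW assessments will not be performed".
- Protocol 9.3: the PD set holds randomised participants who "receive the appropriate dose of study treatment and have CMAP recorded for baseline and at least one post baseline assessment".
- SAP 5.7.2.1: the deviations handled by the hypothetical strategy are "participant received the wrong study intervention and CMAP at Week 28 performed out of a specified time window" (more than 2 weeks off).

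The primary analysis (Protocol 9.4.2.2, SAP 5.7.2.2) is not a t-test. It is an MMRM over the eleven post-baseline visits with baseline CMAP as a covariate, treating missing values as missing at random.

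**The concern.** The power statements are worded as minimums, yet they are computed at the largest sample the design can deliver. The plan names study discontinuation as its key intercurrent event, rules out replacement, removes undosed participants from the PD set and sets aside a badly mistimed Week 28 CMAP. None of this enters the sample size.

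The margin above each minimum is under one point, so on the stated t-test a single complete loss among 45 takes both figures below what is claimed. The joint figure matters most, because the key secondary hierarchy opens only if both primary nulls are rejected. If the shortfall were real and material, the trial would be slightly less likely to reach its secondary tests than its readers were told.

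**Working it through.** **Inputs.** Difference 18, common SD 15, two-sided 5%, 15 per arm (Protocol 9.2, SAP 2.3). The documents give no loss rate, no correlation between visits and no correlation with baseline; any value used for these below is an assumption.

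**Step 1: reproduce the stated figures.** For one comparison, SE = 15 × √(1/n₁ + 1/n₂), noncentrality = 18/SE, df = n₁ + n₂ − 2. With 15 v 15:

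- SE = √(225 × 2/15) = √30 = 5.477
- noncentrality = 18/5.477 = 3.286
- df = 28, critical t = 2.048
- power from the noncentral t = 88.7%

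Under Hochberg, both nulls are rejected when the larger p-value is at most 0.05. Simulating three normal arms, with the two t-tests sharing the Dysport arm, gives 81.3% jointly. Both stated figures reproduce, with margins of about 0.7 and 0.3 points.

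**Step 2: treat each loss as total.** The pooled column uses one variance from all three arms (df = N − 3), which is closer to the planned model. For a single loss, the per-comparison figure is for an affected comparison.

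| Usable at Week 28 (Dysport/Botox/Xeomin) | Two-sample t: per comparison / both | Three-arm pooled: per comparison / both |
|---|---|---|
| 15/15/15 | 88.7% / 81.3% | 89.4% / 82.5% |
| 14/15/15 | 87.5% / 79.6% | 88.4% / 81.0% |
| 15/14/15 | 87.5% / 80.3% | 88.4% / 81.6% |
| 14/14/14 | 86.3% / 77.7% | 87.2% / 79.2% |
| 13/13/13 | 83.5% / 73.6% | 84.5% / 75.4% |

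The pooled joint figure for one Dysport loss sits on the 81% line and cannot be told from it within simulation error.

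**Step 3: credit earlier visits.** A dosed participant lost before Week 28 can have up to seven earlier post-baseline visits (Day 7 to Week 24). As an illustration, let R be the correlation of those visits with Week 28 and n₁ the number observed at Week 28 out of 15 per arm:

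variance of an arm mean = (225/n₁) × (1 − R²(15 − n₁)/15), df = 3n₁ − 3.

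- n₁ = 14, R = 0.6: (225/14) × (1 − 0.36/15) = 15.69, giving 88.0% / 80.3%
- n₁ = 14, R = 0.8: (225/14) × (1 − 0.64/15) = 15.39, giving 88.6% / 81.2%
- n₁ = 13, R = 0.6: 86.2% / 77.8%
- n₁ = 13, R = 0.8: 87.5% / 79.7%

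This treats R as known, so it is a guide and not an exact MMRM power.

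**Step 4: credit the baseline covariate instead.** Take 14 per arm as total losses, with no credit for earlier visits and one further df spent (38). The variance of an arm mean is (225/14) × (1 − r²). With r = 0.2 this is 15.43, giving 88.4% / 81.0%; with r = 0.3 it is 14.63, giving 90.0% / 83.4%.

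**Step 5: compare with the planning inputs.** On the stated t-test at 15 per arm, an SD of 16 instead of 15 gives 84.5%, and a difference of 17 instead of 18 gives 85.0%. Either costs more than one total loss in every arm (86.3%).

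**The case for a change.** The strongest case for acting is that both documents cite a t-test, and on that test one complete loss falsifies both minimums. Neither document offers the MMRM as its reason for omitting a loss allowance. Recovery is nil for anyone randomised but not dosed, because such a participant has no post-baseline data. With two losses per arm, even the favourable correlation of 0.8 leaves both figures short (87.5% and 79.7%).

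All of that is accurate. What stands is that the complete-data condition is unwritten. The rest weighs less:

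- Total loss is the extreme case. Randomisation and injection share Day 1, so non-dosing should be rare. A Week 28 CMAP more than 2 weeks off schedule would normally come from someone with all earlier visits.
- The joint figure is already tied in the text to 15 per arm.
- Judging the minimums on the t-test alone ignores the baseline adjustment and the repeated measures of the analysis that will be run.

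The design remedies do not earn their place either. Stopping at 45 dosed would not restore 15 per arm: under Protocol 6.3.1 the next participant takes the next number in sequence, which may belong to another arm, and 14/16/15 still gives about 80.4% jointly on the stated t-test. Randomising 16 per arm means 3 more volunteers (48 in all) to protect about 2 points per comparison (88.7% against 86.3%) and 3 to 4 jointly (81.3% against 77.7%) from a loss whose frequency nobody has stated.

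**Conclusion.** The concern does not call for a change. The stated 88% and 81% are right for 15 per arm with a usable Week 28 CMAP. What is missing is a sentence saying that they assume no loss between randomisation and Week 28.

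With one loss per arm, the shortfall against the stated figures under the planned type of analysis runs from nothing to about 2 points. The upper end comes from total losses with pooled variance (87.2% and 79.2%). The lower end comes from visit correlations near 0.8 or a baseline correlation of about 0.2. These correlations and the loss itself are assumptions, so a breach is not established. Two losses per arm would bring both figures below the stated minimums under every visit correlation tried, but power per comparison would remain at 83.5% or more.

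Type I error, the treatment estimates and the testing order are the same whether or not the sentence is added. The authors could add it as a courtesy to readers, with any loss rate labelled as an assumption; nothing in the design or analysis depends on it.

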9.3 Analysis Sets

For the purposes of analysis, the following analysis sets are defined:

Participant Analysis Set	Description
Screened	All participants who signed an informed consent form
Randomised	The randomised set will contain all participants who are randomised to study treatment. A participant will be considered as randomised if a study intervention group has been randomly assigned. For analyses and displays, participants will be classified according to randomised treatment
Safety	The safety set will contain all participants who receive at least one dose of study medication. For analyses on the safety set, participants will be classified according to treatment received. If there is any doubt whether a participant was treated or not, he will be assumed treated for the purposes of analysis.
Pharmacodynamic (PD)	The PD analysis set will contain all participants from the randomised set who receive the appropriate dose of study treatment and have CMAP recorded for baseline and at least one post baseline assessment.

9.4 Statistical Analyses

The statistical analysis plan (SAP) will be finalized prior to database lock and it will include a more technical and detailed description of the statistical analyses described in this section. This section is a summary of the planned statistical analyses of the most important endpoints including primary and key secondary endpoints.

The COVID-19 pandemic may have an impact on this study. Participants substantially affected directly or indirectly by COVID-19 will be flagged with a protocol deviation. If the protocol deviation is major and is suspected to interfere with CMAP total amplitude, it will be handled as intercurrent event as described in Section 9.4.2.1. Further details will be provided in the SAP.

Statistical analyses will be performed by an external CRO, managed by the sponsor's biometry department. Statistical evaluation will be performed using Statistical Analysis System (SAS)[®] version 9.4 or higher.

9.4.1 General Considerations

Subject disposition will be summarized descriptively for all screened subjects. Discontinuations will be summarized descriptively for all randomized subjects. Demographics and other baseline characteristics will be summarized descriptively in the randomized set by study intervention group and overall.

Data collected in this trial will be summarized according to their nature as follows:

- Continuous variables: arithmetic mean, standard deviation, minimum and maximum values, median and quartiles depending on the number of observations.
- Categorical variables: absolute and relative frequencies.

A summary table of protocol deviations and the corresponding listing will be prepared.

9.4.1.1 Pharmacodynamic Evaluation

Individual pharmacodynamic endpoints will be tabulated by treatment and timepoint. For the EDB CMAP, three measurements of CMAP will be taken at each timepoint including baseline. The mean of these three measurements will be used to determine the parameter relative change from baseline in CMAP total amplitude, used in primary and secondary analyses of the EDB CMAP related endpoints. The baseline value used for the analyses will be the average of six measurements, the three measurements at screening and the three measurements at baseline.

At each visit time to latency will be evaluated. Skin temperature and stimulation intensity will be also collected for quality control and descriptive statistics.

Individual pharmacodynamic endpoints will be tabulated by treatment allocation and timepoint. Further details on general statistical considerations will be specified in the statistical analysis plan (SAP).

